The study will enroll participants to complete a brief open-label clinical trial of a probiotic dietary supplement. Individuals who provide informed consent and are eligible for participation will attend three study visits. At Visit 1, the research team will collect data on demographics, substance use, and medical history. Eligibility will be determined using the criteria listed below. Blood samples will be taken by a licensed healthcare provider. Eligible participants will complete a one-hour magnetic resonance imaging (MRI) scan, to occur on a separate day due to MRI scheduling constraints. Participants will receive a 30-day supply of the probiotic supplement with dosing and storage instructions. Participants will be instructed to take the standard dosage of 2 probiotic capsules per day. Participants will be asked to respond to a daily query from the research team confirming that they have taken their daily probiotic dose. Visit 2 will be scheduled 15 days (plus or minus 5 days) after the initiation of the probiotic supplement. The research team will collect blood samples and assess alcohol consumption since Visit 1, protocol adherence, and potential side effects. Participants will attend Visit 3 upon completion of the probiotic supplement, to occur 30 days (plus or minus 5 days) after initiation. Data will be collected as described for Visit 2, plus participants will complete a final one-hour MRI scan. Visit 4 will take place 1-10 months after completion of the study probiotic as a "washout" time point. A blood sample and substance use assessment will be collected at Visit 4. Appointments will take place at the Center for Alcohol and Addiction Studies lab space in the School of Public Health, and MRI scans will be conducted at Brown's Magnetic Resonance Imaging Facility (MRF).

Data to be collected at each session is described below.

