- Visit 1 (Baseline Screening & MRI): Breath alcohol content (BrAC) will be measured using a handheld digital sensor to confirm BrAC of .00 g% at the time informed consent is obtained. Age, weight, pregnancy status, urine drug metabolites, recent alcohol use, treatment-seeking status, MRI safety/compatibility, safety for blood draw, basic medical history, and medication use will be assessed per Eligibility Criteria listed in Section 4. The research team will check the individual's state-issued photo ID to verify age and identity. Height and weight will be measured using a standard scale. Urine samples will be collected to test for presence of drug metabolites. Urine samples from participants who are able to become pregnant will be tested for pregnancy hormones. Basic demographic information, social history, and health-related data will be collected on questionnaires. Questionnaires on alcohol use and related symptoms (Alcohol Use Disorders Identification Test; AUDIT) will be administered. Blood samples will be taken for testing of biomarkers per the research aims. The Timeline Followback (TLFB) measure will be used to assess alcohol use in the past 30 days. Current or recent seeking of treatment for alcohol or drug use will be assessed. Participants will be interviewed for history of major medical conditions and current medication usage. Because it is necessary to confirm eligibility prior to MRI scanning and because advance notice is needed for MRI scheduling, participants will be asked to return on a separate day to complete a one-hour MRI scan of the brain at Brown's MRI Research Facility. Participants who are able to become pregnant will be given a urine pregnancy test prior to MRI scanning. BrAC of .00 g% will be confirmed prior to the MRI scan. Eligible participants will be given a 30-day supply of the probiotic supplement with dosing and storage instructions. The research team will collect contact information and request permission to send daily emails to confirm participants' adherence to the study protocol.
- Visit 2: Participants will complete questionnaires on side effects and adherence to the study protocol. Blood samples will be taken for testing of biomarkers. BrAC of .00 g% will be confirmed prior to study procedures.

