### Procedures for a Positive Breath Alcohol Reading (BrAC):

In the event that a participant has a positive BrAC reading, the visit will be rescheduled for another date. If a participant has a repeated positive BrAC reading, the participant will be withdrawn from the study. If a participant's BrAC exceeds the legal limit for operating a motor vehicle (>.08%) at any visit, the person will be asked to wait at the research site until the BrAC reading is under .08%. The person will be offered a rideshare for transportation home at study expense.

**4. Participant Population.** In order to approve research, the IRB must determine that the selection of participants is equitable and reasonably related to the purpose and aims of the research. The IRB must also consider whether adequate safeguards are in place to minimize any risks that are unique to vulnerable populations. To make this determination, the IRB must review all methods and materials used to contact and recruit potential participants, including letters, flyers, emails, etc.

Human participants will be healthy, non-treatment-seeking adult heavy drinkers recruited from the community. Participants will not be asked or encouraged to change their alcohol use as part of the study. Up to 100 individuals will be enrolled to obtain a final sample of 15 individuals to complete the study. The sample size is appropriate for a pilot study intended to generate preliminary data for future full-scale work. Full eligibility criteria are listed below.

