## 6. Compensation / Reimbursement

Participants will be compensated for their time and effort as follows: \$50 for Visit 1 screening (approximately 2.5 hours) and \$50 for Visit 1 MRI (approximately 1.75 hours); \$30 for Visit 2 (approximately 1.5 hours); \$80 for Visit 3 (approximately 3 hours); \$1 per day for each day the participant responds to emails about adherence (maximum \$30); \$40 for Visit 4 (approximately 1.5 hours). Participants found not eligible to complete the study at Visit 1 will be given compensation prorated at \$20/hour. Participants will be offered reimbursement for parking and/or transportation as needed. Payments will be made by electronic gift card, specifically an Amazon gift card. The compensation rate of approximately \$20/hour is appropriate for the time, effort, and activities involved in participation. Participants will be paid at the completion of each visit. For the daily response compensation, participants will be paid at the end of the 30-day period for the total of days that they responded.

- 7. Potential Research Risks / Discomforts to Participants. In order to approve the research, the IRB must consider the risks posed to participants by the research and any efforts to mitigate those risks. The IRB needs to determine that the risks have been both minimized and are reasonable in relation to the anticipated benefits to participants, as well as to the importance of the knowledge that may be gained. The IRB will also consider whether the informed consent process provides potential participants with an accurate and fair description of the risks or discomforts.
- 1. Risk of side effects from probiotic supplementation: The study will utilize a commercially available probiotic supplement product (Seed DS-01™ Daily Synbiotic) that has an excellent safety and tolerability profile. The most common side effects of probiotics are abdominal bloating and/or gas, which typically dissipate after the first few days of use. The Seed DS-01™ Daily Synbiotic undergoes rigorous quality control testing for contaminants (e.g., heavy metals, pesticides) and allergens (e.g., nuts, gluten, milk) and is the subject of ongoing independent clinical trials for irritable bowel syndrome and post-antibiotic recovery. The product is vegan, preservative-free, and free of common allergens (soy, dairy, gluten). Probiotic supplements are not regulated by the FDA or subject to IND requirements.

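### Baseline blood and drinking history come from the screening session with no limit on the time to first dose, and no drinking history is scheduled on the baseline scan day

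*Combined protocol and SAP*

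**What the plan says.** Part III, section 3 (Materials, Methods and Analysis) treats Visit 1 as one visit but describes two attendances. The screening procedures include "Blood samples will be taken for testing of biomarkers per the research aims" and "The Timeline Followback (TLFB) measure will be used to assess alcohol use in the past 30 days". The scan comes afterwards: "participants will be asked to return on a separate day to complete a one-hour MRI scan of the brain". The stated reasons are that eligibility must be confirmed first and that scanner slots need advance notice. The summary paragraph of the same section agrees that the scan is "to occur on a separate day due to MRI scheduling constraints". Section 6 (Compensation / Reimbursement) pays for the two sessions separately, at about 2.5 and 1.75 hours.

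On the scan day the listed checks are a pregnancy test where relevant and "BrAC of .00 g% will be confirmed prior to the MRI scan". Handing over the product is listed after the scan in both places, but neither names the day of dispensing or of the first dose.

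Later visits use a different anchor. "Visit 2 will be scheduled 15 days (plus or minus 5 days) after the initiation of the probiotic supplement", and Visit 3 falls 30 days, give or take 5, after the same point. At Visit 3 the TLFB, blood and scan belong to one visit, and the TLFB there runs from Visit 1. At Visit 4 it again covers 30 days.

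The SAP models plasma markers at Visits 1, 3 and 4. The time-varying covariates kept are heavy drinking days, drinking days and days since last drink. It describes no MRI analysis.

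No sentence states outright that blood and TLFB fall on the screening day. That is inferred from the order of the text and the two-session structure; nothing places either on the scan day.

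**The concern.** In an open-label within-subject study the baseline stands in for a control group. Its value depends on how closely it describes the participant at the start of treatment. Here the baseline blood is tied to screening and the follow-up blood to initiation, and nothing limits the time between the two anchors. An illness, a course of antibiotics or a change in drinking in that interval enters the pre/post difference. Antibiotic use in the past month is an exclusion, but no re-check before the first dose is described.

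Two further consequences concern drinking data. The SAP adjusts the plasma models for recency of drinking, so the investigators regard it as relevant, yet the baseline scan day has no scheduled measure of it beyond a zero breath reading. And if the Visit 3 recall starts at screening, the gap is added to its window, so a count of drinking days can rise when drinking has not changed.

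**Working it through.** The plan gives no figure for the lag, so there is none to reproduce. The check compares the two ends of the schedule and then does calendar arithmetic.

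**1. The two ends side by side (Part III, section 3)**

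| | Baseline | Visit 3 |
|---|---|---|
| Blood | with screening procedures | at the visit |
| TLFB | with screening procedures, past 30 days | at the visit, from Visit 1 |
| MRI | later, separate day | at the visit |
| Timing relative to first dose | no limit stated | 25 to 35 days after |

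**2. Interval from baseline blood to Visit 3**

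Let g be the days from the screening session to the first dose. The documents do not give g, so the values below are assumptions. If the listed order is followed, g is at least 1, because the scan is on another day and dispensing follows it; g = 0 is shown only for reference.

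- Interval = g + 25 to g + 35 days, nominally g + 30. If the TLFB recall starts at screening, this is also the Visit 3 recall window.
- Ratio to the 30-day windows at Visits 1 and 4 = interval / 30.
- Share of the nominal window before the first dose = g / (g + 30).
- Nominal Visit 3 count for someone with an unchanged 4 heavy drinking days per 30 days (the floor of inclusion criterion 3A, used as an illustration) = 4 × (g + 30) / 30.

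| g (assumed) | Window, days | Ratio to 30 | Share before first dose | Heavy-day count, no real change |
|---|---|---|---|---|
| 0 | 25–35 | 0.83–1.17 | 0% | 4.0 |
| 7 | 32–42 | 1.07–1.40 | 19% | 4.9 |
| 14 | 39–49 | 1.30–1.63 | 32% | 5.9 |
| 28 | 53–63 | 1.77–2.10 | 48% | 7.7 |

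**3. What this does to the plasma model**

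The SAP enters heavy drinking days and drinking days as counts and states no conversion to rates. Days since last drink is not affected by window length. At g = 14 the unchanged drinker's heavy-day count rises by 5.87 − 4.00 = 1.87. If b is the coefficient for heavy drinking days, other covariates held aside, the adjusted Visit 3 contrast shifts by −1.87b with no change in drinking or in the marker. For a marker that rises with drinking (b > 0), that shift looks like benefit. The documents do not give b.

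**4. Drinking recency at the baseline scan**

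Visit 1 is defined to include both sessions, so a recall that starts at Visit 1 can be read in two ways.

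- Counted from screening: the later TLFB covers the days between screening and scan, so the last drink before the baseline scan is recoverable, but only by recall weeks afterwards, and the Visit 3 window lengthens as in step 2.
- Counted from the scan day: the days between the screening TLFB and the scan are covered by neither recall. The window lengthens only by the time from scan to first dose.

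Each reading leaves one of the two problems, and the plan does not say which applies. The summary paragraph also has drinking since Visit 1 assessed at Visit 2, but the Visit 2 list names no drinking measure and the SAP uses Visits 1, 3 and 4 only.

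**The case against.** The strongest reply is that, for the outcome the SAP analyses, the baseline is sound. Blood and TLFB come from the same session, both precede treatment, and drinking is a time-varying covariate. The split visit has practical reasons, and any single-arm study carries the risk of intercurrent illness throughout the treated month as well. Most of that stands: the baseline pair is matched, and drinking is at least partly adjusted for. It does not answer the absence of a cap, which adds an untreated interval of unknown length to the period at risk, nor the unequal recall windows on which the adjustment rests.

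Several stronger readings are tempting but not supported:

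- A reader might infer that the first dose is undated. Visits 2 and 3 are timed from initiation and dosing is queried daily, so a date should be obtainable. What is missing is a schedule linking it to baseline.
- A reader might infer that the baseline scan has no drinking data at all. Breath alcohol is confirmed beforehand, and a later TLFB may cover the gap. What is missing is a TLFB or last-drink date on the day.
- A reader might infer that participants could start capsules before the scan. Both descriptions list dispensing after it. The order is not stated as a rule, but nothing suggests that it was broken.
- A reader might infer that the SAP requires days since last drink for the MRI comparison. It has no MRI analysis, so the scan point bears on Aim 2 only as the protocol states it.
- A reader might set the 16 who started against the ceiling of 100 enrolled, to suggest many unnecessary blood draws. The ceiling is not a count of people screened or bled, and callers are prescreened by telephone.

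It is also fair to say that the SAP reports a completed cohort, so a reordered visit cannot help those data. The analysis part of the fix can.

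**Conclusion.** The point holds as a weakness of schedule and covariate definition. The protocol sets no maximum time from baseline blood to first dose and schedules no drinking history on the baseline scan day, and the SAP does not put drinking counts on a common window. The structure applies to everyone who started the probiotic, but its size cannot be fixed from the documents: 39 to 49 days, and a heavy-day count of 5.9 instead of 4.0, follow only if the gap is 14 days and the Visit 3 recall starts at screening. With a gap of a few days the effect would be small. The conclusion also rests on the inference that blood and TLFB fall on the screening day. It does not invalidate the plasma baseline. It is worth changing because baseline is the only comparator and the change is cheap.

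**What to change.** In the protocol:

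- At the baseline MRI visit, extend the TLFB to that day and record the date of the last drink.
- Draw the baseline biomarker blood at that visit. If it stays at screening, set a maximum interval from blood to first dose.
- State that product is handed over only after the baseline blood and scan are done.
- Say which day Visit 1 means wherever a recall period starts from it.

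In the SAP, define heavy drinking days and drinking days over a fixed 30-day window before each blood sample, or as a rate per day of recall. For data already collected, report the distribution of the interval from baseline blood to first dose and re-run the models with drinking on this common scale; both should be possible from recorded visit and start dates and the daily TLFB entries.

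The cost is a short repeat TLFB, since the screening TLFB is still needed for eligibility, and nurse time on the MRI day if the draw is moved. The number of scans and of blood draws per participant does not change. Keeping the blood at screening with a cap avoids the nurse booking but may mean repeating the draw when a scan slot falls outside the limit.

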## Probiotic Supplement Storage and Dispensing:

The probiotic product will be stored in a locked cabinet in the PI's office until the time of dispensing to
the participant. Participants eligible for the study will receive a 30-day supply with dosing and storage
instructions per the manufacturer. Any unused probiotic products at the end of the study will be
disposed of by the PI by placing the unused product in a waste bin, or taken home by study staff. This
product is not a controlled substance or considered hazardous with regard to storage or disposal.

### Procedures for a Positive Breath Alcohol Reading (BrAC):

In the event that a participant has a positive BrAC reading, the visit will be rescheduled for another date. If a participant has a repeated positive BrAC reading, the participant will be withdrawn from the study. If a participant's BrAC exceeds the legal limit for operating a motor vehicle (>.08%) at any visit, the person will be asked to wait at the research site until the BrAC reading is under .08%. The person will be offered a rideshare for transportation home at study expense.

**4. Participant Population.** In order to approve research, the IRB must determine that the selection of participants is equitable and reasonably related to the purpose and aims of the research. The IRB must also consider whether adequate safeguards are in place to minimize any risks that are unique to vulnerable populations. To make this determination, the IRB must review all methods and materials used to contact and recruit potential participants, including letters, flyers, emails, etc.

Human participants will be healthy, non-treatment-seeking adult heavy drinkers recruited from the community. Participants will not be asked or encouraged to change their alcohol use as part of the study. Up to 100 individuals will be enrolled to obtain a final sample of 15 individuals to complete the study. The sample size is appropriate for a pilot study intended to generate preliminary data for future full-scale work. Full eligibility criteria are listed below.

#### **Inclusion Criteria:**

- 1) 18-64 years of age:
- 2) Able to speak and read English well enough to complete study procedures;
- 3) Meets NIAAA guidelines for heavy drinking in the past 30 days, defined as at least one of the following:
  - A) at least 4 heavy drinking episodes (≥4 drinks for women, ≥5 drinks for men on a given day);
  - B) at least 2 heavy drinking weeks (>7 drinks for women, >14 drinks for men per week).

#### **Exclusion Criteria:**

- 4) Chronic disease requiring daily use of medication;
- 5) Seeking or receiving treatment for alcohol/drug use, with exception of smoking cessation;
- 6) Self-reported history of liver disease:
- 7) Antibiotic or probiotic use in past 1 month, wherein probiotic use pertains only to supplements and not to foods that contain probiotics such as yogurt, kefir, kimchi, etc.;
- 8) Positive urine test for amphetamine, cocaine, methamphetamine, opioids, or benzodiazepines (cannabis use will be assessed but is not an exclusion criterion);
- 9) History of fainting, weakness, infection, excessive bruising, or extreme distress from blood draw;
- 10) Safety contraindication for MRI (e.g., ferromagnetic implant in the body, claustrophobia);
- 11) History of head trauma with loss of consciousness >10 min;
- 12) For people able to become pregnant: Pregnant, breastfeeding, or not using effective birth control;
- 13) Unable to complete the study visits due to time or scheduling constraints;
- 14) Weight <110 lbs (due to blood draw guidelines).
- 15) Conditions of immunodeficiency, such as HIV infection, primary immune deficiency, or taking immune-suppressant medications.

v. 6/5/2020 Page **7** of **19** 

Vulnerable Populations: Vulnerable populations (e.g., fetuses, pregnant women, prisoners, children) will **not** be included in this study.

#### 5. Recruitment Methods

Participants will be recruited from the general community using print or online advertisements (Google), flyers posted in public venues, listservs (Brown University listservs), postings on social media (Facebook), Today@Brown postings, and online bulletin boards (Craigslist). Contact information will be provided for follow-up. Interested individuals who contact the study will complete a brief (10-minute) telephone prescreening interview administered by research staff. Individuals will be prescreened by phone to assess key eligibility criteria and interest in participation. Information collected from the prescreening interview will not be retained for research purposes. Before beginning the interview, staff will confirm that the caller is in a private location. Ineligible individuals will be informed of their ineligibility and thanked for their interest. Eligible individuals will be scheduled for Visit 1. The PI and Research Assistant will complete all applicable training in human subjects research protections prior to recruiting participants. The study will be advertised as not providing treatment or medication, such that the probiotic supplement should not be confused with clinical care.

## 6. Compensation / Reimbursement

Participants will be compensated for their time and effort as follows: \$50 for Visit 1 screening (approximately 2.5 hours) and \$50 for Visit 1 MRI (approximately 1.75 hours); \$30 for Visit 2 (approximately 1.5 hours); \$80 for Visit 3 (approximately 3 hours); \$1 per day for each day the participant responds to emails about adherence (maximum \$30); \$40 for Visit 4 (approximately 1.5 hours). Participants found not eligible to complete the study at Visit 1 will be given compensation prorated at \$20/hour. Participants will be offered reimbursement for parking and/or transportation as needed. Payments will be made by electronic gift card, specifically an Amazon gift card. The compensation rate of approximately \$20/hour is appropriate for the time, effort, and activities involved in participation. Participants will be paid at the completion of each visit. For the daily response compensation, participants will be paid at the end of the 30-day period for the total of days that they responded.

- 7. Potential Research Risks / Discomforts to Participants. In order to approve the research, the IRB must consider the risks posed to participants by the research and any efforts to mitigate those risks. The IRB needs to determine that the risks have been both minimized and are reasonable in relation to the anticipated benefits to participants, as well as to the importance of the knowledge that may be gained. The IRB will also consider whether the informed consent process provides potential participants with an accurate and fair description of the risks or discomforts.
- 1. Risk of side effects from probiotic supplementation: The study will utilize a commercially available probiotic supplement product (Seed DS-01™ Daily Synbiotic) that has an excellent safety and tolerability profile. The most common side effects of probiotics are abdominal bloating and/or gas, which typically dissipate after the first few days of use. The Seed DS-01™ Daily Synbiotic undergoes rigorous quality control testing for contaminants (e.g., heavy metals, pesticides) and allergens (e.g., nuts, gluten, milk) and is the subject of ongoing independent clinical trials for irritable bowel syndrome and post-antibiotic recovery. The product is vegan, preservative-free, and free of common allergens (soy, dairy, gluten). Probiotic supplements are not regulated by the FDA or subject to IND requirements.
- 2. Risks of MRI scan: MRI has no known side effects and does not involve radiation. However, there are several contraindications for MRI scan. The first is metallic materials within the body, such as aneurysm clip, bullet or shrapnel fragment, ear implant, certain prosthetic devices, heart pacemaker, or artificial heart valve. Participants will be thoroughly screened, first by the researcher and again by the MRI technician, to prevent

v. 6/5/2020 Page **8** of **19** 

admission of individuals with these contraindications to the MRI suite. The second contraindication is pregnancy, as risks to the fetus are unknown. Pregnancy tests will be administered to all participants able to become pregnant at the baseline assessment and again on the days of MRI scanning. Aside from medical contraindications, there is risk of subjective discomfort from being in a small space or from noise emitted by the scanner. Participants will be given a call button to hold during the MRI so that they can communicate distress to the MRI technician and research staff, and procedures can be discontinued if indicated. Participants will be required to wear earplugs to reduce exposure to noise from the scanner.

- 3. Psychological discomfort associated with assessment: Participants will be advised during the informed consent process that they may choose not to answer any particular question, that their verbal and written responses are confidential, and that they are free to withdraw from the study at any time. All data collection procedures will be performed in private rooms reserved for these purposes.
- 4. Breach of confidentiality of personal identifiable information (PII): Several steps will be taken to protect against loss of confidentiality. All data will be collected and stored using technology that employs the highest industry standards for security. Data will be stored in de-identified, password-protected files on Brown University's secure servers. Participant data and samples will be identified using a unique study ID code not related to their PII. Participants' personal identifying information will be kept in a separate location from their response data. At the conclusion of the study, the file that contains links of personal identifiers with unique study IDs will be destroyed by the study PI. Biological samples will be identified with the participant's study ID and will not be associated with PII. With these precautions, loss of confidentiality is considered very unlikely; however, participants will be informed of the potential risk at the time they provide consent.
- 5. Risks associated with blood draw procedures. During the informed consent process, participants will be advised of the necessity of obtaining blood samples throughout the trial. The study will exclude individuals who report physical or psychological discomfort caused by blood draw or the sight of blood, or who report history of excessive bruising, fainting, or weakness following standard blood draw procedures. Blood draw procedures will follow World Health Organization guidelines for safe and well-tolerated procedures to minimize risk of infection or other complications. A licensed research nurse will collect the blood samples. Risk reduction strategies are to use sterile, single-use implements; surface disinfectant; proper hand hygiene; application of 70% isopropyl alcohol to the blood draw site; minimal vein probing; application of pressure after drawing blood; and non-latex, vinyl gloves.
- 6. Risk of coercion from compensation received for participation: The risk of coercion from compensation for participation is low, as the total amount of compensation is modest. The hourly compensation rate for the study sessions translates to approximately \$20/hour, which is consistent with rates offered by similar studies in the Brown University area and is intended to offset the effort required of participants outside of study sessions (i.e., daily adherence to the probiotic protocol).
- 7. Risk of adverse reaction to the probiotic supplement: In the unlikely event that a participant reports adverse reaction to the probiotic beyond the mild side effects noted in #1 above, the participant will be instructed to discontinue the probiotic and will be withdrawn from the study.

Standard of Care: There is no established "standard of care" for healthy heavy drinkers who are not seeking treatment. The probiotic supplement does not replace or otherwise alter any clinical care that participants would receive. At the conclusion of the study, participants will be given an NIAAA pamphlet on the risks of heavy drinking.

v. 6/5/2020 Page **9** of **19** 

DSMP/DSMB: The DSMP is attached and contains information on the DSMB.

8. Potential Benefits of the Research. NOTE: Compensation for participation is not a benefit and should not be included in this section. In order to approve this research, the IRB must determine that the potential benefits to research participants are reasonable in relation to the potential risks. Very often, research at Brown does not include potential direct benefits to participants, but may only benefit society as a whole by helping researchers.

Some individuals experience a noticeable benefit in health when using probiotics. Many subjects in this study are unlikely to benefit directly from participation. Benefits to society are expected to accrue through generation of scientific knowledge about effects of probiotics on inflammation in heavy drinkers.

